1. The subject experiences/presents with ocular signs or symptoms worse than those encountered during routine contact lens wear (e.g., a slit lamp sign of \geq Grade 3). It is up to the Unmasked Examiner to determine when an Adverse Event Form should be completed.
2. At every visit, the Unmasked Examiner must ask the subject's parent or guardian, in these exact words, "Has your child experienced any changes in his or her eyes, vision, or health since the last visit?"

The Unmasked Examiner should document an adverse event in response to this question if:

1. the condition is chronic, not previously documented, and requires a change in medications or change in daily activities over an extended period, or
2. the examiner feels it is acute and warranted, such as a broken bone or head trauma (not warranted is cold, flu, or ear infection).

All information that the parent expresses should be noted in the Other Examination Information box in REDCap. Whether or not an Adverse Event Form should be completed is determined by the Unmasked Examiner, after asking appropriate follow-up questions.

For example, if a parent says that her child had a headache, the Unmasked Examiner should ask appropriate questions to determine the quality, frequency, onset, location, duration, associations, relief, and severity of the headache. After hearing the responses to the questions, the clinician should use his or her best judgment to determine whether or not this may be related to study treatment. If the Unmasked Examiner believes that it may be related to the study treatment, then an Adverse Event Form should be completed.

3. The Unmasked Examiner should ask the parent the precursor question about items in the Symptom Checklist at the beginning of each visit form after Baseline, "Have you or your child noticed any of the following symptoms related to his or her eyes since the last visit?"

Each symptom should be read, and the parent and/or child should answer "yes" or "no" to each symptom. If the answer is "yes," then appropriate follow-up questions should be asked so that the Unmasked Examiner can determine whether or not the symptom may be related to the study treatment and therefore an Adverse Event Form should be completed.

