Final decision of whether or not each event is an Adverse Event will be decided by the Executive Committee during weekly conference calls. In general, if the Unmasked Examiner is unsure of whether or not something should be categorized as an adverse event, an Adverse Event form should be completed. When completing the Adverse Event Form, the Unmasked Examiner should **not** include information about the subject's treatment group assignment, so that the Executive Committee's decision of whether or not something is an Adverse Event is less likely to be potentially biased.

Categorization of an Adverse Event

The following sections help to categorize the adverse event. If the event is serious or unexpected, then special reporting is required. Otherwise, complete an Adverse Event Form and submit it to the Data Coordinating Center as soon as possible.

Type of Adverse Event

- **Ocular:** Pertaining to the eye and adnexa
- **Non-ocular:** All other events

Significance

- **Serious:** Any adverse event that is fatal or life threatening, is permanently disabling (two line or more loss of best-corrected visual acuity), requires subject hospitalization or prolongs hospitalization, or results in a congenital anomaly or birth defect.
- **Non-serious:** all other events

Severity

- **Mild:** Events that lead to easily tolerated signs or symptoms that do not change normal activities or require treatment with prescription medications (may require over-the-counter medications)
- **Moderate:** Events that lead to signs or symptoms that may interfere with daily activities and/or are treated with prescription medication
- **Severe:** Events that are usually incapacitating or sight-threatening and generally require prescription medication

Would Contact Lens Wear Have Been Discontinued?

Regardless of whether the subject discontinues contact lens wear, the unmasked examiner should determine whether s/he would have discontinued contact lens wear in that situation. For example, a subject may have discontinued contact lens wear for two days while she had a fever. If the doctor determines s/he would not have recommended discontinuation contact lens wear, then the answer would be No.

- **No:** Doctor would not have discontinued contact lens wear
- **Yes, temporarily:** Doctor would have temporarily discontinued contact lens wear
- **Yes, permanently:** Doctor would have permanently discontinued contact lens wear

Was Event Unexpected?

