• **Ocular:** An event is *expected* if it is on the list of potential complications from contact lens wear presented in the parental permission document OR is an occasional ocular finding in a pediatric population (eg, flashes, floaters, or atrophic retinal hole); otherwise, the event is unexpected. Expected events with contact lens wear include:

- Burning, stinging, and or itching of the eyes
- Less comfort after all day wear
- A feeling like there is something in the eye
- Inflammation of the cornea (clear window on the front of the eye) and/or scratch of the cornea
- Swelling of the cornea
- Small blood vessels growing into the cornea
- Small defects in the corneal surface (corneal staining)
- Redness
- Bumps on the inside of the eye lid (tarsal abnormalities)
- Inflammation of the inner eye (iritis)
- Excessive watering, unusual eye secretions, or redness of the eye
- Blurred vision
- Rainbows or halos around objects
- Sensitivity to light

- Dry Eyes
- **Non-Ocular:** An event is *unexpected* if it meets *all* of the following criteria:
 1. unexpected (in terms of nature, severity, or frequency) given the research protocol, informed consent document, and subject population
 2. related or possibly related to participation in the research
 3. suggests that the research places subjects or others at a greater risk of harm than was previously known or recognized

Related or Unrelated

- **Definitely Related:** An adverse event that has a timely relationship to the administration of the investigation procedure and follows a known pattern of response for which no alternative cause is present.
- **Probably Related:** An adverse event that has a timely relationship to the administration of the investigation procedure and follows a known pattern of response, but for which a potential alternative cause may be present.
- **Possibly Related:** An adverse event that has a timely relationship to the administration of the investigation procedure and follows no known pattern of response, but a potential alternative cause does not exist.
- **Unrelated:** An adverse event for which there is evidence that it is definitely related to a cause other than the investigation procedure; in general, no timely relationship to the administration of the procedure exists, or if so, the event does not follow a pattern of response and an alternative cause is present.

Prompt Submission of an Adverse Event to the IRB

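### The relatedness scale runs backwards: Possibly Related bars a potential alternative cause that Probably Related allows, so some timely events fit no category

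*Combined protocol and SAP*

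**What the plan says.** Chapter 32, under Related or Unrelated, builds four grades from three attributes: timing relative to the investigation procedure, fit to a known pattern of response, and alternative cause.

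- *Definitely Related*: timely, and "follows a known pattern of response for which no alternative cause is present".
- *Probably Related*: timely, and "follows a known pattern of response, but for which a potential alternative cause may be present".
- *Possibly Related*: timely, and "follows no known pattern of response, but a potential alternative cause does not exist".
- *Unrelated*: the lead clause requires that "there is evidence that it is definitely related to a cause other than the investigation procedure". A second clause then describes the general case: the event is not timely, "or if so, the event does not follow a pattern of response and an alternative cause is present".

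There is no unknown or residual grade, and Chapter 32 gives no rule for events that meet none of the four or more than one.

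The grade has a use within the same chapter. Under Was Event Unexpected?, a non-ocular event must meet three criteria to count as unexpected, and one is that it is "related or possibly related to participation in the research". Categorization of an Adverse Event then states: "If the event is serious or unexpected, then special reporting is required".

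**The concern.** A relatedness scale should loosen as it descends. Here an alternative cause that is only potential is tolerated at the second grade and prohibited at the third.

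The two upper grades also both need a known pattern of response. An effect not previously recognised has none, so Possibly Related is the only related grade open to it, and any potential alternative cause closes that one. The filing step uses a more lenient standard: the Unmasked Examiner is to "determine whether or not this may be related to study treatment", and if it may be, a form is completed. An event can therefore be recorded because it may be related and then find no related grade that admits it.

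At stake are the special-reporting route for non-ocular events that are not serious, and the consistency of any table by relatedness. Two examiners could grade the same event differently and both be following the text.

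**Working it through.** The plan gives no figure to reproduce, so the check sets the four definitions against every combination of their attributes.

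**Inputs**, all from Related or Unrelated: timely (yes or no); known pattern (yes or no); alternative cause in four states (none, potential only, present but not shown to be definite, present with evidence that it is the definite cause). That gives 2 × 2 × 4 = 16 combinations. A cause that is present is taken to be also a potential one, so it too rules out Possibly Related.

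*Unrelated* can be read in two ways:
- Reading A: the lead clause (evidence of a definite other cause) is necessary.
- Reading B: the general clause is sufficient without it.

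| Timely | Known pattern | No alternative cause | Potential only | Present, not definite | Definite |
|---|---|---|---|---|---|
| Yes | Yes | Definitely | Probably | Probably | Probably and Unrelated |
| Yes | No | Possibly | **no category** | A: none; B: Unrelated | Unrelated |
| No | Yes | A: none; B: Unrelated | A: none; B: Unrelated | A: none; B: Unrelated | Unrelated |
| No | No | A: none; B: Unrelated | A: none; B: Unrelated | A: none; B: Unrelated | Unrelated |

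**Combinations without a category**
- Reading A: 2 timely + 3 + 3 not timely = 8 of 16.
- Reading B: 1 of 16.

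The cell in bold is empty under both readings: timely, no known pattern, alternative cause only potential. It is not Possibly Related, because a potential cause exists. It is not Unrelated by the lead clause, because nothing shows a definite other cause. It is not Unrelated by the general clause either, because that clause asks for a cause that is present.

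The neighbouring cell (present, not definite) shows the conflict inside Unrelated: the lead clause refuses the event and the general clause takes it. The overlap at top right arises if the lead clause alone is enough for Unrelated. If both clauses are required, that event is Probably Related only, and the count without a category stays at 8.

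**Effect of rewording Possibly Related alone**, so that it admits a potential or present cause not shown to be definite:
- Reading A: 8 − 2 = 6 of 16 left, all non-timely events without a definite other cause.
- Reading B: 1 − 1 = 0 of 16 left, but the present-not-definite cell would then be both Possibly Related and Unrelated.

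So the rewording is not enough by itself. The lead clause of Unrelated has to govern, and the six non-timely cells need a stated rule.

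**Route to reporting.** Take a non-serious, non-ocular event in the bold cell. It has no related grade, so on that grading it does not meet the relatedness criterion, is not unexpected, and does not trigger special reporting. Ocular events do not follow this route: their expectedness rests on the list of lens complications and on occasional paediatric findings, and seriousness is defined without reference to relatedness.

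**The case against.** The strongest case on the other side is that this is a slip of wording with little practical effect.

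- Clinicians would probably read Possibly Related in the sensible way. That may be so, but nothing in the documents shows that this was the intended meaning, and the text as it stands is the operative rule.
- On the more generous reading of Unrelated only 1 of 16 combinations is empty. This stands as a caution about the count, which depends on the reading. That one cell is nevertheless empty on either reading.
- Other provisions limit the harm. A form is to be completed when the examiner is unsure whether something is an adverse event. The DSMC reviews reported adverse events whatever their grade (Chapter 33). Each local IRB sets its own rule for prompt reporting. All of this stands and keeps the effect small.
- The link to reporting is partly inferred. The criterion for unexpected non-ocular events speaks of taking part in the research, whereas the scale speaks of the investigation procedure, and relatedness is only one of three criteria that must all be met. This also stands.
- The documents specify no analysis by relatedness, so no planned result is shown to be wrong.

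These points bear on size. None of them makes the four definitions consistent.

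**Conclusion.** The inconsistency is real. Possibly Related has a stricter test on alternative cause than Probably Related. A timely event with no known pattern and a merely potential other cause fits no category. Where the other cause is present but not definite, the clauses of Unrelated contradict each other.

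A reader might go further and infer that any conceivable other cause sends such an event to Unrelated. The wording does not support that: the lead clause needs evidence of a definite other cause, and the general clause needs a cause that is present. A conceivable cause leaves a gap, and Unrelated is reached only by elimination. A reader might also infer a systematic undercount of related events. The documents give neither event frequencies nor an analysis by relatedness from which to establish one.

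The size is 8 of 16 logical combinations without a category on the strict reading and 1 of 16 on the loose one. These are not proportions of events. The practical consequence is confined mainly to non-ocular events that are not serious, and to any tabulation by relatedness. It rests on two assumptions: that the relatedness criterion for unexpected events is answered from this scale, and that a present cause counts as a potential one.

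**What to change.** In Chapter 32, Related or Unrelated:

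1. Reword *Possibly Related* to a timely relationship with no known pattern of response, where a potential alternative cause may be present but is not shown to be the definite cause.
2. Make evidence of a definite other cause the governing test for *Unrelated*, and reconcile the general clause with it. State which grade applies when a timely event with a known pattern also has a definite other cause.
3. State how non-timely events without a definite other cause are coded. A blanket default of every unclassified event to Possibly Related is not needed and could dilute that grade.
4. Recheck the relatedness coding of Adverse Event Forms already filed, without reference to arm. The chapter already tells examiners to leave treatment assignment off the form. It describes the Executive Committee's decision only as whether something is an adverse event, so the revision should name who rechecks relatedness.

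The cost is a short rewording and one recoding pass over existing forms. The downside is that a few more events will be counted as possibly related.

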| 7/29/14 | Pages 84 and 85: Remove Chapter 32: Study Forms |
| 7/29/14 | Page 36: Changed the Equipment section to read: “Measurement of pupil diameter is performed using the NeuroOptics VIP-200 Pupillometer (NeuroOptics, Inc., Irvine, CA) prior to the instillation of any mydriatic or cycloplegic drops while the subject is uncorrected. The objective of the measurement is to estimate the habitual pupil size during contact lens wear. Measurements should be performed at Visits 1, 5, 7, and 9. For the mesopic condition, the subject should stand facing the examiner with his or her back toward the wall-mounted visual acuity chart. The room lights should be off except for the incandescent lamp over the examination chair at the opposite end of the room. For the photopic condition, the subject should stand facing the examiner with his or her back toward the wall-mounted visual acuity chart, and the visual acuity chart illumination should be turned on and be the same as when taking visual acuity measurements (approximately 75 – 120 cd/m ² or 9.3-9.9 EV; see Chapter 13).” |
| 7/29/14 | Page 48: corrected the gaze and corresponding retina, and made the order the same as will be measured. |
| 7/29/14 | Page 15: Added + Acc Lag (Visit 1) to Table 8-2. |
| 7/29/14 | Page 27: Changed what to wear after the over-refraction from new lens power to spherical over-refraction in trial frame and habitual contact lens |
| 7/29/14 | Page 34: Remove depth from corneal staining description |
| 7/29/14 | Page 72: Allowed Contact Information Form to be maintained in subject binder instead of separate file. |
| 7/29/14 | Page 47: Add accommodative lag chapter |
| 7/29/14 | Page 36: Added that the light which should be pointed straight down toward the examination chair during the mesopic condition. |
| 7/29/14 | Page 74: Added, “Subjects should be encouraged to wear their contact lenses during all waking hours, but they should also be reminded that they can wear their glasses any time they wish.” |
| 7/31/14 | Page 15: Moved Choroidal Thickness in Table 8-2 to right after contact lens movement |

| | |
|----------|--|
| 7/31/14 | Chapter 20: Clarified lag measurement at baseline protocol |
| 7/31/14 | Page 14: Removed "at near" from VA requirement with +2.50 add |
| 7/31/14 | Chapter 26: Added chapter on contact lens insertion, removal and care |
| 7/31/14 | Page 15: Moved Choroidal Thickness in Table 8-2 from Visit 1 to Visit 2 |
| 8/25/14 | Page 56: Changed "22" to "18" because of mis-numbering |
| 8/25/14 | Page 37: Changed first visit OCT is performed to Visit 2 instead of Visit 1 |
| 8/25/14 | Page 34: Changed slit lamp grading to Efron scale for all slit lamp signs |
| 8/25/14 | Pages 38-44: Replaced Chapter 18 to improve clarity of procedure and include uploading information |
| 8/25/14 | Page 7: Added [name] to Study Group and dates of participation |
| 8/25/14 | Page 60: Add how to upload file into REDCap |
| 2/13/15 | Page 14: Added, "If a subject is ineligible, the Study Completion Form should be completed (in REDCap) with the reasons for the ineligibility." |
| 2/13/15 | Page 19: Added, "At this time, complete the discontinuation section of the Study Completion Form in REDCap." |
| 2/13/15 | Pages 34, 58, 59, and 72: change "mode" to "median" for ridding autorefractor readings of errant values. |
| 2/13/15 | Page 26: added section "High Contrast Monocular Visual Acuity at Baseline |
| 2/13/15 | Page 48: stated that forehead rest should be used during central autorefraction. |
| 2/13/15 | Page 88: add a section stating how it will be determine whether or not an Adverse Event Form should be completed, and who will make the final determination of whether or not it is an Adverse Event. |
| 2/16/15 | Page 28: trial lenses should be used to conduct an over-refraction instead of a phoropter. |
| 3/18/15 | Page 35: Changed the wording about when an adverse event report should be completed to match the adverse event chapter. |
| 8/21/15 | Page 67: Replaced steps 7-10 with updated text. |
| 9/1/15 | Page 60: Changed analysis diameter in COAS from 5 mm to 6 mm |
| 11/30/15 | Page 7: Updated study personnel |
| 12/14/15 | Pages 97-89: Replace chapter on adverse events to make categorization more clear |
| 12/29/15 | Page 15: CISS will be completed only at Visits 1, 3, 4, 5, 7, and 9 |
| 2/18/16 | Table 25-1: CISS will be completed only at Visits 1, 3, 4, 5, 7, and 9 |
| 3/24/16 | Page 53: Added, "Any reading on the Lenstar that is highlighted in red is not valid. Readings highlighted in red must be deleted and, if possible, replaced with a valid reading. If it is not possible to obtain five valid readings for a measurement location, a protocol deviation form should be completed, documenting that readings highlighted in red were deleted and could not be replaced with valid ones." |
| 6/2/16 | Page 46: Added tetracaine |
| 10/13/16 | Page 83: Added section on protocol for submitting manuscripts |
| 10/13/16 | Page 88: Added section on prompt reporting of adverse events to IRB |
| 10/13/16 | Page 12: Updated personnel |
| 1/3/17 | Page 27: Allowed for phoropter to be used for over-refraction |
| 1/30/17 | Page 83: Included grant support from UH Core Grant in acknowledgments (P30-EY007551) |
| 5/4/17 | Page 7: Added [name] to the study group |
| 5/18/17 | Page 90: Inserted Chapter 34: BLINKlink Phase |
| 5/18/17 | Page 91: Changed Chapter 34: Bibliography to Chapter 35: Bibliography |
| 5/18/17 | Page 92: Changed Chapter 35: MOP Changes to Chapter 36: MOP Changes |
| 5/31/17 | Page 7: Updated study personnel |
| 7/31/17 | Page 7: Updated study personnel |

| | |
|---------|---|
| 8/23/17 | Page 7: Updated study personnel |
| 8/29/17 | Page 83: Included grant support from UH Core Grant in acknowledgments (UL1 TR 001070) |
| 5/18/18 | Page 7: Updated study personnel |
